4.2 SCIENTIFIC RATIONALE FOR STUDY DESIGN

This is a pragmatic study that seeks to evaluate in real-world practice the use of a CHE and PN intervention to improve the uptake of evidenced-based HPV vaccinations. Thus, it uses a post-design to evaluate participants' changes in knowledge and intentions to vaccinate by comparing

outcomes at baseline to outcomes after exposure to the CHE educational intervention. Similarly, it uses a post-test design to evaluate the uptake of the HPV vaccine after participating in the PN intervention. In real-world practice it is important to measure an intervention's impact not only at the patient-level but also at the clinic- and system-level. Consequently, we will measure post-intervention the rates of the HPV vaccine 1st dose, 2nd dose, and/or 3rd dose uptake for each clinic and for the DHHA systems by comparing its rates to state level HPV vaccine rates.

4.3 END OF STUDY DEFINITION

This study will end when the minimum number of participants (400 participants) for analyses is recruited. The protocol will be closed once data analysis and publications have been completed.

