1 PROTOCOL SUMMARY

1.1 SYNOPSIS

Protocol Title: *Intervention to Educate and Improve Underserved Populations' Participation in Clinical Trials and the Uptake and Completion of the HPV Vaccine Series*

Objectives:

- **Primary Objective:**
 - 1) *Educate parents (and young adults) via CHEs about the HPV vaccine, in order improve knowledge and intentions to increase uptake of the vaccine for individuals aged 9-26.*
 - 2) *We will collect socio-demographic data to explore its association with knowledge, intentions, & vaccine uptake.*
- **Secondary Objectives:**
 - 1) *Increase completion of the HPV vaccine via PN to promote uptake of one, two, or three vaccine doses among adolescents and young adults (9-26 years old).*
 - 2) *Assess intervention delivery and patient-, clinic-, and system-level impact of the PN intervention to increase vaccine completion among adolescents and young adults.*

Endpoint:

- **Primary Endpoint:**
 - 1) *Knowledge and intentions to initiate or complete the HPV vaccine series among project participants.*
 - 2) *Association of sociodemographic variables (e.g., age, gender, ethnicity, health insurance, income, zip code) to knowledge, intentions, and uptake of the HPV vaccine among participants*
- **Secondary Endpoints:**

- 1) *Uptake of one, two, or three HPV vaccine doses among adolescents (9 to 17 years of age)*
- 2) *Uptake of one, two, or three HPV vaccine doses among young adults (18-26 years of age).*

- ***Tertiary/exploratory:***

- 1) *To assess PN impact we will record the number of participants to whom the PN scheduled to, a) receive a recommended 1st dose, 2nd dose, or 3rd dose of the HPV vaccine; b) connect to care services such as health insurance, discount or no-cost HPV vaccine programs, and c) facilitate other services such as language translation, appointment scheduling assistance, transportation services, and childcare.*
- 2) *To assess patient-level impact, we will track for each participant their (a) baseline HPV vaccine doses, and (b) the number of those they obtained in total, and quarterly (c) the number of patients who received a 1st dose, 2nd dose, or 3rd dose of the HPV vaccine.*

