- 3) *To assess clinic-level impact, we will obtain clinic vaccination reports track the number of patients at each clinic who received: (a) 1st dose, 2nd dose, or 3rd dose of the HPV vaccine at baseline; and record quarterly: (b) 1st dose, 2nd dose, or 3rd dose of the vaccine broken by age for adolescents (9 to 17 years old) and young adults (18-26 years old).*

Population:

- ***Sample size***

- *Maximum number of participants that can be enrolled is 1000*
- *Minimum number of participants to be enrolled 400 (number of participants needed for analyses)*

Phase: N/A

Participating Sites: Denver Health and Hospital Authority

Description of Study

Intervention: Education and Patient Navigation

[figure not shown]
Study Duration: 36 months

Participant Duration:

Duration will vary for each participant and will be determined by vaccination status. Participants will be contacted to complete a post-education at baseline using the NCI survey. We will only administer the survey pages 1-3.

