5.5 STRATEGIES FOR RECRUITMENT AND RETENTION

HPV Educational Intervention: To recruit participants we will distribute flyers regarding our educational events about HPV and the HPV partnering with each outpatient clinics at DHHA. Additionally, The PN and CHE will be fully onboarded at DHHA to access patient records, including upcoming clinic visits to identify potential participants who are eligible for the HPV vaccine. Thus, the PN will be able to call participants that meet the eligibility criteria and will recruit them to participate in the study. All participants will be identified through their own patient record. Young adults (18–26-year-old) will be contacted directly and invited to participate in the study. For individuals under the age of 18 (9–17-year-old), we will use the patient's record to obtain parent contact information and invite the parent to participate in the study. Parents might indicate having additional children that are older than 18 years of age when completing surveys. For those parent participants we will capture vaccinations status on all their children aged 9–26, even if those children are not DH patients. However, the survey will not collect any PHI on children from parent participants, only vaccinations status. To assess uptake of the HPV vaccine from children participants and young adult participants, we will use their DH medical record number to determine vaccination status after the educational and patient navigation intervention has been delivered. Additionally, for parent and adult participants, who volunteer to participate, we will collect name, phone number, mailing address, and email address for follow up at 3- and 6-months intervals if they report not having been vaccinated themselves or their eligible aged children (9–17) at baseline and/or at the 3-month follow up interval.

In order encourage participants to answer our surveys, we will incentivize them by compensating them with a \$25 gift for filling the post-education survey at baseline.

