7.3 LOST TO FOLLOW-UP

The evaluation of the educational intervention occurs at baseline during the post education survey. Our sample size of 200 will achieve 80% power the moment the 200th participant completes the post survey at baseline. Thus, lost to follow-up is not a concern in our study. Follow-up is only to capture vaccination status, as well as to facilitate patient navigation if it applies. Furthermore, follow-up will only occur for some participants. Only those that indicate at baseline not being vaccinated themselves or indicate being parents of children that have not been vaccinated will be contacted at 3 months post baseline. Similarly, only those that indicate not being vaccinated themselves or indicate having children not being vaccinated at 3 months post baseline will be contacted at 6 months post baseline. For those that are contacted at 3 months and 6 months, we will make a maximum of 6 contacts (e.g., phone calls, texts, or letters) to each consented participant. After 6 unsuccessful contact attempts, we will consider participant as “lost to follow up” and no longer make attempts to contact them.

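### Section 4.3 ends the study at the 400th recruitment, before late enrollees' 3- and 6-month contacts, and the secondary uptake endpoint has no counting time

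*Protocol*

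**What the plan says.** **End of study.** Section 4.3 has two sentences. The first is the trigger: "This study will end when the minimum number of participants (400 participants) for analyses is recruited". The second concerns administrative closure: "The protocol will be closed once data analysis and publications have been completed". The synopsis (1.1) adds "Study Duration: 36 months", not divided into accrual and follow-up, and lets each participant's duration depend on vaccination status.

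**Follow-up.** Section 5.5 collects contact details for "follow up at 3- and 6-months intervals if they report not having been vaccinated themselves" or their eligible children. Section 7.3 describes a 3-month contact and then, for month 6, says that "only those that indicate not being vaccinated themselves or indicate having children not being vaccinated at 3 months post baseline will be contacted". It also says that follow-up exists to record vaccination status and to support navigation. Section 8.1 gives a wider 6-month trigger, adding people who did not attend for a booked dose. Section 8.2.4 books needed doses at both times.

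**The uptake endpoint.** The synopsis and section 3 name uptake of one, two or three doses, by age group, with no time attached. Section 4.2 says "it uses a post-test design to evaluate the uptake of the HPV vaccine after participating in the PN intervention". Section 5.5 uses the Denver Health record number "to determine vaccination status after the educational and patient navigation intervention has been delivered". Among the exploratory items, the synopsis counts each participant's baseline doses and "the number of those they obtained in total", together with quarterly counts of patients by dose.

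**The concern.** Anyone enrolled less than 6 months before the 400th recruitment cannot have reached the 6-month contact when that recruitment occurs, and the last recruits cannot have reached either contact. Section 7.3 ties follow-up to vaccination status, so the part of the study that falls after the stated end is the part that serves the secondary endpoint.

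The missing counting time adds to this. Uptake, series completion and the 0/1 adherence variable in section 9.4.1 all depend on when the record is read: a person partway through a series can be non-adherent on one date and adherent on a later one. Without a common time, a reported proportion mixes participants observed for years with participants observed for days, and its value depends partly on the shape of recruitment.

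**Working it through.** The protocol gives no figure for follow-up time or for the precision of uptake. Its one power statement (section 9.2) concerns the primary outcome and is not in dispute: an exact paired t-test calculation with 200 participants, effect size 0.20 and two-sided 0.05 gives 80.4%, against the stated 80.0%.

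**Step 1: end of study against follow-up.**

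| Section | Event | Timing |
|---|---|---|
| 4.3 | Study ends | 400th recruitment |
| 4.3 | Protocol closes | After analysis and publication |
| 5.5, 7.3, 8.1 | Contacts | 3 and 6 months after baseline, conditional on vaccination status (8.1 adds a missed dose) |
| 8.2.4 | Needed doses booked | 3 and 6 months |

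For the 400th participant, both contacts come after the first row. The second row does not say that contact or dose capture continues until closure.

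**Step 2: is the endpoint dated anywhere?**

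- 1.1 and 3: no time.
- 4.2 and 5.5: after the intervention, with no date or window. Section 6.2 runs navigation until the series is complete, so its end differs between people.
- 1.1, quarterly patient-level counts: exploratory, not the secondary endpoint.
- 8.2.5: mentions completion at the 3- or 6-month follow-up, but as a rule for ending navigation.
- 8.2.6: a quarterly column for navigation follow-up and clinic rates, and no column for month 3 or month 6.

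So the protocol has times at which doses may be captured, but does not say which of them defines the endpoint.

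**Step 3: illustration of unequal observation.** Inputs: N = 400 (4.3). Two assumptions are not in the protocol: dose capture stops at the 400th enrolment, and accrual is uniform over A months. The share with under t months of observation is t/A, and the number is 400 × t/A.

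| A (assumed) | Under 6 months | Under 3 months |
|---|---|---|
| 36 | 6/36 = 16.7% (67) | 3/36 = 8.3% (33) |
| 24 | 6/24 = 25% (100) | 3/24 = 12.5% (50) |
| 12 | 6/12 = 50% (200) | 3/12 = 25% (100) |

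Accrual shape matters too. At A = 36, linearly falling accrual gives (6/36)² = 2.8% (11 people) under 6 months, and linearly rising accrual gives 1 − (30/36)² = 30.6% (122 people). Conversely, if recruitment finished by month 30 and capture ran to month 36, nobody would have under 6 months.

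Under each assumed pattern, the count is an upper bound on missed contacts, because contact is conditional on vaccination status.

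**Step 4: room for a 6-month window.** If accrual now fills 36 months, the rate is 400/36 = 11.1 per month. Finishing by month 30 needs 400/30 = 13.3 per month, which is 20% faster. If accrual is already planned to finish by month 30, no change is needed.

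**The case against.** The best defence is that section 4.3 is loosely worded and means the end of enrolment. Its trigger is a recruitment count, its second sentence keeps the protocol open through analysis, and the follow-up sections make no exception for late enrollees. That may well be the intention. But the section is the end-of-study definition, and no passage says that follow-up or record capture outlasts it, so the wording needs correcting either way.

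A second defence is that doses are captured quarterly and at months 3 and 6, and that an extraction date can be left to an analysis plan. The capture schedule exists and deserves credit. The exact extraction cut-off is indeed SAP material. The time at which an endpoint is assessed is part of its definition, however, and here it interacts with a stopping rule that the protocol does fix.

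Three stronger readings are tempting and are not supported:

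- A reader might infer that late enrollees' doses will be lost. Section 5.5 reads status from the medical record, so they remain recoverable. What is missing is when the record is read.
- A reader might treat the 36 months as a second, conflicting end rule. It is a planned duration, and a planned duration can coexist with an event trigger.
- A reader might take the percentages above as expected loss or bias. They depend on an assumed capture stop and an assumed accrual pattern.

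**Conclusion.** The point holds as a matter of wording with consequences for the secondary and exploratory results. Taken literally, section 4.3 ends the study before the last enrollees' planned vaccination-status follow-up, and no passage gives the uptake endpoint a counting time. Uptake proportions would therefore rest on unequal time to receive a dose. The primary outcome comes from the baseline post-education survey and is untouched.

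No size of bias can be derived. The illustrative share with under 6 months of observation, 17% to 50%, requires capture to stop at the 400th enrolment and uniform accrual over 36 down to 12 months. Other accrual shapes move it in either direction, and it is zero if capture continues for 6 months after the last enrolment.

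Two smaller points in section 7.3 belong here. Its dismissal of loss to follow-up rests only on the baseline survey, although the same section goes on to define when a participant counts as lost. Its 6-month contact trigger is also narrower than the one in section 8.1.

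**What to change.** 1. In the endpoint definitions (1.1 and 3), state one common look-up time after baseline for dose counts from the Denver Health record. Apply it to every index patient, whatever the contact or survey response. The protocol's own 6-month point is one example. Because section 8.2.4 still books doses at that contact, report later doses separately.
2. Use the same time for the adherence variable in section 9.4.1.
3. Amend section 4.3 so that enrolment closes at the target and the study ends once the last participant's look-up has been made. Check that this fits the 36 months in 1.1.
4. In section 7.3, limit the statement about loss to follow-up to the baseline survey.
5. Reconcile the 6-month contact triggers in sections 7.3 and 8.1. Which of them should stand is for the investigators.

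**Cost.** Wording changes, plus one record extraction per participant from a system the team already uses. Data capture would run past the last enrolment by the length of the chosen window. Earlier completion of recruitment (13.3 rather than 11.1 per month for a 6-month window) or a longer stated duration is needed in full only if accrual currently fills the 36 months.

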5 STUDY POPULATION

5.1 INCLUSION CRITERIA

In order to be eligible to participate in this study, an individual must meet all of the following criteria:

Denver Health Patients:

1. Be a Denver Health patient* 18-26 years old, who has not started or completed the HPV vaccine series (Vaccine completion for this age group is 3 doses).
2. Be a parent of a Denver Health adolescent patient* aged 9-17 years old (), who has not started or completed the HPV vaccine series. (Vaccine completion is 2 doses for 9-14-year-old, and 3 doses for 14-17-year-old)
3. English and/or Spanish Speaking
4. Stated willingness to comply with all study procedures and be available for the duration of the study.

* Denver Health patients will be identified from one of the following clinics: Denver Health Clinics Eastside Adult Clinic, Eastside Women's Care Clinic, Westside Adult Clinic, Westside Women's Care Clinic, Pavilion C: Women's Care Clinic, La Casa-Quigg Newton Family Health Center, Lowry Family Health Center, Montbello Family Health Center, Westwood Family Health Center, Parkhill Family Health Center, Webb Center For Primary Care, Pena Southwest Clinic

5.2 EXCLUSION CRITERIA

An individual who meets any of the following criteria will be excluded from participation in this study:

1. Individuals who do not meet eligibility criteria, including individuals who do not speak English or Spanish [at the discretion of the CHE or PN upon recruitment]
2. Decisionally-challenged adults with cognitive or personality impairment or due to intoxication (alcohol or drugs) that might interfere with their ability to consent or participate in the study [at the discretion of the CHE or PN upon recruitment]
3. Individuals from vulnerable populations (e.g., inmates, homeless, pregnant women, and those with auditory impairment [at the discretion of the CHE or PN upon recruitment]
4. Individuals under the age of 18 years.

5.5 STRATEGIES FOR RECRUITMENT AND RETENTION

HPV Educational Intervention: To recruit participants we will distribute flyers regarding our educational events about HPV and the HPV partnering with each outpatient clinics at DHHA. Additionally, The PN and CHE will be fully onboarded at DHHA to access patient records, including upcoming clinic visits to identify potential participants who are eligible for the HPV vaccine. Thus, the PN will be able to call participants that meet the eligibility criteria and will recruit them to participate in the study. All participants will be identified through their own patient record. Young adults (18–26-year-old) will be contacted directly and invited to participate in the study. For individuals under the age of 18 (9–17-year-old), we will use the patient's record to obtain parent contact information and invite the parent to participate in the study. Parents might indicate having additional children that are older than 18 years of age when completing surveys. For those parent participants we will capture vaccinations status on all their children aged 9–26, even if those children are not DH patients. However, the survey will not collect any PHI on children from parent participants, only vaccinations status. To assess uptake of the HPV vaccine from children participants and young adult participants, we will use their DH medical record number to determine vaccination status after the educational and patient navigation intervention has been delivered. Additionally, for parent and adult participants, who volunteer to participate, we will collect name, phone number, mailing address, and email address for follow up at 3- and 6-months intervals if they report not having been vaccinated themselves or their eligible aged children (9–17) at baseline and/or at the 3-month follow up interval.

In order encourage participants to answer our surveys, we will incentivize them by compensating them with a \$25 gift for filling the post-education survey at baseline.

6 STUDY INTERVENTION

6.1 STUDY INTERVENTION(S) ADMINISTRATION

6.1.1 STUDY INTERVENTION DESCRIPTION

The educational intervention to be delivered by the CHE consists of “toolkit education materials” developed by the National Cancer Institute (NCI) and a small media intervention (i.e., video) that our research team has developed. The NCI-produced toolkit education materials consist of Power Point presentations, flyers, and posters that contain information about HPV, HPV-related cancers, and the importance of the HPV vaccine series for adolescents (9-17 years old) and young adults (18-26-year-old) who are eligible for the vaccine.

6.2 STUDY INTERVENTION COMPLIANCE

Study participants who volunteer to participate in this study will be asked to comply with the following interventions strategies:

1. Watch or participate in approximately a 45-minute educational session conducted by the CHE.
2. Receive a referral to the PN if they and/or their children are eligible for the HPV vaccine but have not completed all the recommended HPV vaccine series doses.
3. Receive navigation for the number of HPV vaccine series doses needed until completion.

7 STUDY INTERVENTION DISCONTINUATION AND PARTICIPANT DISCONTINUATION/WITHDRAWAL

7.1 DISCONTINUATION OF STUDY INTERVENTION (STUDY STOPPING RULES)

The Sponsor-Investigator has the right to terminate this study at any time. Reasons for terminating the study may include, but are not limited to, the following:

- The incidence or severity of adverse events in this or other studies indicates a potential health hazard to patients.
- Patient enrollment is unsatisfactory.

7.2 PARTICIPANT DISCONTINUATION/WITHDRAWAL FROM STUDY

Participants are free to withdraw from participation in the study at any time upon request. In addition, the investigator has the right to withdraw a patient from the study at any time. Reasons for withdrawal from the study may include, but are not limited to, the following:

- Patient withdrawal of consent at any time
- Any medical condition that the Sponsor-Investigator determines may jeopardize the patient's safety if he or she continues in the study.
- Sponsor-Investigator determines it is in the best interest of the patient
- Patient non-compliance

Every effort should be made to obtain information on patients who withdraw from the study. The primary reason for withdrawal from the study should be documented on the appropriate eCRF.

7.3 LOST TO FOLLOW-UP

The evaluation of the educational intervention occurs at baseline during the post education survey. Our sample size of 200 will achieve 80% power the moment the 200th participant completes the post survey at baseline. Thus, lost to follow-up is not a concern in our study. Follow-up is only to capture vaccination status, as well as to facilitate patient navigation if it applies. Furthermore, follow-up will only occur for some participants. Only those that indicate at baseline not being vaccinated themselves or indicate being parents of children that have not been vaccinated will be contacted at 3 months post baseline. Similarly, only those that indicate not being vaccinated themselves or indicate having children not being vaccinated at 3 months post baseline will be contacted at 6 months post baseline. For those that are contacted at 3 months and 6 months, we will make a maximum of 6 contacts (e.g., phone calls, texts, or letters) to each consented participant. After 6 unsuccessful contact attempts, we will consider participant as “lost to follow up” and no longer make attempts to contact them.

